8.1.2 Schedule of Additional Assessments for PK Subgroup ONLY

Visit(s)	2	2b ²	8b ³
Time point	Day 0	Day 1 ²	(Week 20) ³
Blood Sampling Window (±)	≤ 60 minutes Predose	23 hours ± 60 minutes Postdose	23 hours ± 60 minutes postdose
Blood sample(s) for PK evaluation	X ¹	X	X ³
IOP measurement ⁴		X	X
SLE ⁵		X	X
Adverse event reporting		X	X

Abbreviations: IOP = intraocular pressure; PK = pharmacokinetic; SLE = slit lamp examination.

Notes:

1. Day 0 PK blood sampling must be performed ≤ 60 minutes before the first IVT injection of study medication.
2. Day 1 PK blood sampling must be performed 23 hours (± 60 minutes) after the IVT injection (ie, first dose of study medication).
3. Week 20 PK blood sampling must be performed 23 hours (± 60 minutes) after the IVT injection (ie, sixth dose of study medication).
4. IOP is measured by tonometry in the study eye only. Non-contact tonometry may be used, but in the event IOP is greater than 36 mm Hg, it is recommended to perform another IOP measurement with Goldmann or Tonopen or ICare (applanation tonometer) within the next 30 minutes.
5. Slit lamp examination of the anterior segment is conducted in the study eye only.

8.2 Discussion of Study Design

8.2.1 Study Design

The objectives of this study are to demonstrate the equivalence¹¹ of Xlucane to Lucentis® and to evaluate the safety and efficacy of Xlucane as compared to Lucentis® (ranibizumab injection). This will be done through a multicenter, randomized, double-blind (double-masked), parallel group study. The rationale for the design of this trial is to appropriately evaluate Xlucane as compared to Lucentis®, the reference standard for wAMD.

The selected endpoints for demonstrating equivalence of Xlucane to Lucentis® are in accordance with current standards, as are the safety endpoints of the trial. Masking subjects and designated study team members to the treatment assignment(s) ensures objectivity and minimizes bias. Randomization through the IWRS guards against selection bias.

The selected dosing schedule of the 2 study drugs is based upon clinical studies with Lucentis®, whereby monthly dosing is expected to maintain visual acuity and to result in an additional average 1 to 2 letter gain. Furthermore, prespecified safety evaluations will monitor subjects for any adverse events and injection site reactions (ISRs) during and after treatment.

Biosimilarity will be concluded if the two-sided 90% (US FDA) or 95% (ROW) confidence interval (CI) for the difference in mean change in BCVA at Week 8 between the Xlucane and Lucentis® is confined within the equivalence margin of ± 3.5 letters. The difference in the approach around the confidence interval is based on the regulatory requirement in United States (90% CI) and the rest of the world (95% CI), as agreed with the relevant regulatory authorities.

A meta-analysis of ANCHOR¹⁸ and MARINA¹⁰ studies was done in order to focus on Week 8 BCVA data and ensure that the proposed equivalence margin will preserve at least 50% of the lower limit of the 95% confidence interval for the difference in mean change in BCVA between treatment and placebo which was 7.7 (Table 2).

Table 2 Meta-analysis wAMD Ranibizumab Studies using BCVA change at 8 weeks

Study	Experimental			Control			95% CI			Weight (fixed)				
	N	Mean	SD	N	Mean	SD	MD	lower	upper					
MARINA	240	5.4	9.3	238	-2.2	8.4	7.6	6.09	9.11	62.9%				
ANCHOR	139	9.8	11.83	143	-1.8	15	11.6	8.08	15.12	37.1%				
379			381											
									95% CI					
									MD	lower	upper			
									9.08	7.70	10.47			
									Fixed effects model					

An equivalence margin of ± 3.5 letters represents at least 55% of the lower limit of the 95% confidence interval of treatment benefit (7.7 letters) demonstrated above.

Considering this and that the minimal clinically important difference in VA has previously been set to or estimated to be 5 to 10 letters,^{12,13,14} an equivalence margin of ± 3.5 letters is deemed adequate and supported by EMA/FDA in recent scientific advice.

As the primary objective of the study is to demonstrate equivalence of Xlucane versus Lucentis®, a symmetrical equivalence region of ± 3.5 letters will be used. Biosimilarity will be concluded if the two-sided 95% or 90% CI for the difference between Xlucane and Lucentis in the BCVA change from Baseline at Week 8 is confined within the equivalence margin of ± 3.5 letters.

The study is also aimed to detect any notable differences in plasma ranibizumab levels between the 2 products, Xlucane and Lucentis®. Systemic ranibizumab exposure is very low after IVT injection, and there are potential issues in detecting such low levels by an assay. Further considering the approach that any notable differences are more easily detectable at steady-state, when ranibizumab concentrations are higher (ie, near the expected T_{max} after dosing, which is around 22 hours), the current study has PK measurements at Baseline, Day 1 (23 hours [± 60 minutes] after the first dose), and at Week 20 (23 hours [± 60 minutes] after the sixth dose) to possibly detect any differences in peak systemic exposure between the 2 products.

The rationale for the design of this trial is to appropriately evaluate Xlucane as compared to Lucentis®, the current standard of care for wAMD. The clinical relevance for selecting the endpoints of BCVA (using ETDRS) and changes in CFT, area of CNV,

and leakage from CNV lesion(s) is founded upon multiple studies.⁵ Similarly, in Lucentis® clinical studies, VA was measured at a distance of 4 meters (or less) relative to ETDRS. Increased retinal thickness (ie, CFT) and leakage from CNV are well associated with wAMD. All are common causes of severe vision loss and thus changes in these measures can be considered objective endpoint evaluations for wAMD.

Refer also to [Section 6.2](#) of the protocol.

8.3 Selection of Study Population

8.3.1 Number of Planned Subjects

It is anticipated that approximately 580 subjects will be enrolled and randomized.

There are approximately 160 sites anticipated to participate in approximately 15 countries in the United States, Europe, the Middle East, and Asia-Pacific.

Refer also to the statistical considerations in [Section 11.4](#), on which the numbers are based.

Rescreening will be allowed for subjects previously determined as screen failures due to inclusion and/or exclusion criteria that could transiently change and do not compromise the subject's safety. Only one rescreen will be allowed per subject. When a rescreen is authorized by the Sponsor or its designee, the subject is to be reconsented, and all screening procedures (ie, laboratory testing, OCT, and color fundus photography [CFP]) should be repeated/completed and provided to the CRC, **with the exception of the FA procedure. Based on the CRC's determination, screening FA may not need to be repeated. Thus, if the CRC deems it appropriate/acceptable, prior FA performed at the time of the screen failure, may therefore be used for eligibility assessment. However if more than 30 days have passed since subject was screen failed, all procedures including FA must be repeated.** Subjects who discontinue the study after Randomization and after receiving study medication are not eligible for rescreening.

8.3.2 Inclusion Criteria

To be eligible for study entry, subjects must satisfy **all** of the following inclusion criteria:

1. Written and signed informed consent form obtained at Screening before any study-related procedures are performed. Patients must be capable of providing their own consent (an impartial witness must be present in case of illiterate patients).
2. Willingness and ability to undertake all scheduled visits and assessments as judged by the investigator.

3. Newly diagnosed, active subfoveal choroidal neovascularization (CNV) lesion secondary to age-related macular degeneration (AMD) in the study eye. *Note:* active CNV indicates the presence of leakage as evidenced by fluorescein angiography (FA) and intra- or subretinal fluid as evidenced by optical coherence tomography (OCT), which *must be confirmed by the central reading center during Screening:*
 - a. The area of CNV must be $\geq 50\%$ of the total lesion area in the study eye, and
 - b. Total lesion area ≤ 9.0 disc areas (DA) in size (including blood, scars, and neovascularization) as assessed by FA in the study eye
4. BCVA of ≤ 73 and ≥ 49 ETDRS letter score in the study eye using the ETDRS chart (20/40 to 20/100 Snellen equivalent) at Screening.
5. Fellow eye should not be expected to need any anti-VEGF treatment for the duration of study participation based on Investigator's decision.
6. Age ≥ 50 years at Screening.
7. Male and female subjects of childbearing potential must be willing to completely abstain or agree to use an appropriate method of contraception from the time of signing the informed consent form and for the duration of study participation through 3 months after the last dose of study drug. See [Appendix 17.1](#) for examples of acceptable contraception. (The investigator and each subject will determine the appropriate method of contraception for the subject during the participation in the study.)
 - a. A woman of childbearing potential is any woman, regardless of sexual orientation, who meets the following criteria: 1) has not undergone a hysterectomy or bilateral oophorectomy or 2) has not been naturally postmenopausal for at least 12 consecutive months (ie, has had menses at any time in the preceding 12 consecutive months).
 - b. A man of sexual potential is any man who has not been surgically sterilized (eg, has not undergone bilateral orchiectomy).

8.3.3 Exclusion Criteria

Subjects will be excluded from the study if **1 or more** of the following exclusion criterion is applicable:

1. Any previous intervention, including pharmacological treatment, laser, and/or surgery for wAMD in either eye; (Exception: Vitamin supplementation for AMD prevention). (In case of end stage wAMD in fellow eye where anatomical and functional status diagnosed on Screening, disqualifies subject from intravitreal anti-VEGF treatment according to local medical standards of care, the previous laser photocoagulation or PDT procedure in fellow eye performed for wAMD treatment is allowed). (This

criterion is not applicable for fellow eye, in case of subjects who have only one eye or the fellow eye fulfills additional criteria specified in [Section 8.3.4](#)).

2. Any previous vitreoretinal surgery in the study eye for any cause.
3. Any previous IVT treatment, including any anti-VEGF medications, steroids, and/or any other investigational medication in either eye.
4. The use of long-acting steroids, either systemic or intraocular in any eye, in the 18 months before planned initiation of study treatment. (Note: Current or planned Iluvien® [fluocinolone acetonide intravitreal], implantation during the study is prohibited.)
5. Subfoveal fibrosis, subfoveal atrophy, and/or scarring extending > 50% of total lesion area in the study eye as assessed by the investigator at Screening and confirmed by the central reading center prior to Randomization.
6. Choroidal neovascularization in either eye due to non-AMD causes (eg, DME, RVO, ocular histoplasmosis, trauma) as assessed by FA and confirmed by central reading center. (This criterion is not applicable for fellow eye, in case of subjects who have only one eye or the fellow eye optical media opacity prevents from taking the FA/OCT/FP images and the fellow eye fulfills additional criteria specified in [Section 8.3.4](#)).
7. Active or recent (within 28 days prior to Randomization) intraocular, extraocular, and periocular inflammation or infection in either eye.
8. History of idiopathic or autoimmune-associated uveitis in either eye.
9. Infectious conjunctivitis, keratitis, scleritis, or endophthalmitis in either eye.
10. Unmedicated intraocular pressure (IOP) \geq 30 mm Hg at Screening in either eye.
11. Topical ocular corticosteroids administered for \geq 30 consecutive days in the study eye within 90 days prior to Screening.
12. Spherical equivalent of the refractive error in the study eye demonstrating more than 8 diopters of myopia.
13. Corneal transplant or corneal dystrophy in the study eye.
14. History of rhegmatogenous retinal detachment in the study eye.
15. History of macular hole in the study eye.
16. Retinal pigment epithelial tear or rip involving the macula in the study eye as assessed by FA and confirmed by the central reading center.
17. Current vitreous hemorrhage in the study eye.
18. Subretinal hemorrhage that is \geq 50% of the total lesion area in the study eye, or if the subretinal hemorrhage involves the fovea is 1 or more DA ($\geq 2.54 \text{ mm}^2$) in size in the study eye, as assessed by FA and confirmed by the central reading center.

19. Other intraocular surgery (including cataract surgery) in the study eye within the 3 months prior to Baseline. The yttrium aluminum garnet [YAG] posterior capsulotomy is allowed no later than 4 weeks prior to Screening.
20. Any concurrent intraocular condition in the study eye (eg, cataract or diabetic retinopathy) that, in the opinion of the investigator, could require treatment during the study period to prevent or treat loss of visual acuity.
21. Significant media opacities (including cataract) in the study eye interfering with BCVA assessment or fundus imaging (FA/FP/OCT).
22. Aphakia or absence of the posterior capsule in the study eye, unless it occurred as a result of a YAG posterior capsulotomy in association with prior posterior chamber intraocular lens (IOL) implantation.
23. Presence of advanced glaucoma or optic neuropathy that involves or threatens the central visual field in the study eye (as judged by the investigator).
24. History of glaucoma filtering surgery or ALT in the study eye (Exception: Laser iridotomy and SLT are allowed).
25. Uncontrolled ocular glaucoma or hypertension in the study eye, defined as IOP \geq 25 mm Hg despite treatment with anti-glaucoma medication.
26. Any previous systemic anti-VEGF treatment (eg, bevacizumab).
27. Contraindication for Lucentis[®] (hypersensitivity to ranibizumab or to any of the study treatment excipients).
28. Current treatment for active systemic infection.
29. Females who are pregnant, nursing, planning a pregnancy during the study, or of childbearing potential and not using a reliable method of contraception (see [Appendix 17.1](#)) and/or not willing to use a reliable method of contraception during their participation in the study. A pregnancy test administered to women of childbearing potential at the Screening Visit (prior to treatment) must be negative for the patient to receive study medication.
30. Participation in another clinical trial within the previous 3 months or any other clinical trial of anti-angiogenic drugs.
31. Reasonable suspicion of other disease or condition that might render the subject at a high risk of treatment complications or otherwise confound interpretation of the study results (as judged by the investigator).
32. *PK subgroup only:* Contraindication for additional blood sampling (as judged by the investigator).

8.3.4 Optic media opacity in one eye (fellow eye)

There may be circumstances where subjects with only one eye or with the fellow eye with opaque optical media preventing from obtaining FA/OCT/FP images, could be considered for study participation. In those cases it is required that: the subject fulfills all study eligibility criteria; fellow eye suffers from visual impairment of BCVA less than 20/200 Snellen equivalent (<50 ETDRS letters); the fellow eye has a known medical history leading to visual impairment; the fellow eye is not expected to be treated during study in any way and the inclusion of the subject in the study is approved by the study Medical Monitor. It must be noted that in such cases the images from the fellow may not be obtained due to optical media opacity, and therefore they do not need to be graded by the central imaging center.

8.3.5 Removal of Subjects From Therapy or Assessments

Subjects may stop study drug for any of the following reasons:

- Subject request (ie, withdrawal of consent)
- Use of nonpermitted concurrent therapy
- Noncompliance with the study drug or study schedule
- Lost to follow-up (defined as at least 2 missed study visits without any medical reason and without any contact with the study subject, despite the documented investigator's efforts)
- Occurrence of adverse events (AEs) not compatible with the continuation of subject participation in the study, in the investigator's opinion, or unacceptable to the subject to continue
- Investigator request
- Intercurrent illness
- Sponsor request
- Treatment failure, as assessed by the treating investigator

Subjects are free to withdraw from the study at any time without providing reason(s) for withdrawal and without prejudice to further treatment. The reason(s) for withdrawal will be documented in the electronic case report form (eCRF).

Subjects withdrawing from the study will be encouraged to complete the same final evaluations (ie, End of Treatment/ Week 52) as subjects completing the study according to this protocol, particularly safety evaluations. The aim is to record data in the same way as for subjects who completed the study.

Reasonable efforts will be made to contact subjects who are lost to follow-up. These efforts must be documented in the subject's file.

The Sponsor has the right to terminate the study at any time in case of serious adverse events (SAEs) or if special circumstances concerning the study drug or the company

itself occur, making further treatment of subjects impossible. In this event, the investigator will be informed of the reason for study termination.

Pregnancy

Subjects will be instructed that known or suspected pregnancy occurring during the study, in subjects or female partners of male subjects, should be immediately confirmed and reported to the investigator, who will then withdraw the pregnant female subject from the study without delay. Subjects should also immediately notify investigators of any pregnancy occurring during the study but which was confirmed only after completion of the study. In the event that a subject is subsequently found to be pregnant after inclusion in the study, any pregnancy will be followed to term, and the status of mother and child will be reported to the Sponsor after delivery.

Full details will be recorded on the withdrawal page of the eCRF, or an SAE report will be completed if the subject has completed the study. Details of the procedures to be followed if a pregnancy occurs are provided in [Section 10.1.4.2.1](#).

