8.4.1 Identity of Study Medication

Based on the design of this protocol, the Principal Investigator (PI) **MUST** oversee proper separation and delegation of unmasked study roles and responsibilities. To ensure the masking of each randomized subject, the PI must delegate tasks to an unmasked treating investigator and ample unmasked support staff to execute protocol instructions.

Xlucane/ Lucentis® for IVT injection is supplied as single-use vial designed to deliver 0.05 mL of 10 mg/mL ranibizumab. (Lucentis® prefilled syringes may be used if needed [eg, if vials are not available].) The details of the study medications are given in [Table 3](#). All study drug will be imported according to the relevant regulatory requirements. **It must be noted that EU-Lucentis® is not FDA approved and is therefore considered an investigational new drug in the United States.**

Table 3 Study Medication Details

Study Medication	Dosage Form and Strength	Manufacturer
Xlucane	Supplied as single-use, 2-cc glass vial containing 2.3 mg of proposed ranibizumab biosimilar in 0.23 mL solution designed to deliver 0.05 mL of 10 mg/mL proposed ranibizumab biosimilar, by intravitreal injection.	Xbrane Biopharma [name] [name] Sweden
EU-licensed Lucentis®	Supplied as single-use, 2-cc glass vial containing 2.3 mg of ranibizumab in 0.23 mL solution designed to deliver 0.05 mL of 10 mg/mL ranibizumab, by intravitreal injection.	Novartis Pharma Stein AG [name] [name] Switzerland

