8.4.6 Masking

Due to the study objectives, the identity of the study treatment assignments will not be known to subjects. Additionally, except for the site designees who are unmasked for the purpose of preparing and administering the study treatments, other research staff will also be masked. Masked study team members will perform efficacy assessments.

There will be no overlap between the masked and unmasked staff members. Access to the randomization codes will be strictly controlled.

The study medications will have caps/stoppers of differing colors and length; however, they will be packaged and labeled in identical outer cartons. Therefore, sites must have the following unmasked team members and their designated back-ups:

- Unmasked personnel to prepare syringes for IVT injection and provide to the unmasked injector, and complete study drug accountability.
- Unmasked injector to perform injection and safety assessments immediately after the injections (but not to participate in the efficacy assessments).

- There will also be masked and unmasked clinical research associates (CRAs) available for the same site. Unmasked CRAs will monitor study drug accountability.

Randomization information for any particular subject may be made available to the investigator only in the event of a medical emergency or an AE that necessitates identification of the study drug for the welfare of that participant. Masking codes should only be broken in emergency situations for reasons of participant safety. Whenever possible, the investigator(s) should always consult with the medical monitor and the Sponsor prior to breaking the masking.

When the masking code is broken, the reason must be fully documented. The reporting requirements for unmasking are the same for reporting an SAE. See also [Section 10.1.4.2.1 Serious Adverse Events](#).

When all subjects have completed their 6-month assessments, an *unmasked* analysis of efficacy (ie, equivalence) and safety endpoints as well as PK and immunogenicity will be performed. The aim of the *unmasked* analysis is to initiate the submission of the application for marketing authorization as agreed with the European Medicines Agency. This analysis will not affect the further conduct of the study.

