9.2.2 Week 2/ Visit 3 (\pm 2 days)

The Week 2 Visit will take place 14 days/ 2 weeks (\pm 2 days) after Visit 2. The following procedures will be performed:

- Record any changes in adverse events and concomitant medications.
- Perform BCVA assessment using the ETDRS at 4 meters, including manifest refraction.
- Perform OCT in the study eye.
- Record any AEs.

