9.2.10 Week 52/ End-of-treatment or Early Withdrawal Visit/ Visit 16 (\pm 5 days)

The End-of-treatment Visit (Week 52/ Visit 16) will take place 28 days (\pm 5 days) after the last injection of study drug *or* at the time of early discontinuation/withdrawal (if applicable). The following procedures will be performed:

- Record any AEs and any changes in concomitant medication since the previous visit.
- Perform a PE. A PE will consist of a routine evaluation of organ systems (including head, ears, eyes, nose, throat, neck, cardiovascular, pulmonary, abdomen, skin, extremities, neurological, lymph nodes, and musculoskeletal). At the Week 52/End of Treatment Visit, the PE will also include a query of the patient to determine if changes in his/her physical condition have occurred since the PE at Screening.
- Perform BCVA assessment using the ETDRS at 4 meters, including manifest refraction.
- Perform FA(images of both eyes should be sent to CRC, grading of study eye only will be done by CRC).
- Perform OCT in the study eye.
- Perform CFP in the study eye.
- Perform SLE of the anterior segment in the study eye.
- Perform dilated fundus examination of the posterior segment in the study eye.
- Record vital signs including blood pressure and heart rate. Systolic and diastolic blood pressure and pulse rate will be measured after patients have been at rest (seated) for at least 5 minutes.
- Collect blood sample for hematology and clinical chemistry tests.
- Collect blood sample(s) for immunogenic (ie, anti-ranibizumab antibodies and NAb) evaluations.

- For females of childbearing potential only, collect urine sample for pregnancy test.
- Measure IOP in **both** eyes, using the Goldmann tonometry method. In the event IOP is greater than 36 mm Hg, it is recommended to perform another IOP measurement with Goldmann or Tonopen or ICare (applanation tonometer).

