11.3.3 Efficacy Endpoints

11.3.3.1 Primary Efficacy Endpoint

The primary endpoint of the study is the change in BCVA letters at Week 8 compared to Baseline using the Early Treatment Diabetic Retinopathy Study (ETDRS) protocol for the study eye.

Due to the increase in protocol deviations related to the COVID-19 pandemic and following the recent ICH E9 (R1) Addendum¹⁹, the primary and secondary estimands of the study related to efficacy are detailed in this section. These estimands were not explicitly defined in earlier versions of the protocol (see [Section 18](#)) but the estimand framework provides a more comprehensive approach to show the impact of Covid-19 in the analysis²⁰. The presence of such IEs in a biosimilarity study may introduce potential bias and a dilution of treatment differences (i.e. increasing the chance of proving equivalence), as such the ordering of the estimands described below (in terms of primary and secondary) are chosen.

For the primary estimand, the scientific question of interest is the between-group difference (Xlucane v Lucentis[®]) in the mean change from baseline in BCVA letter score at Week 8 in patients who fulfil the study eligibility criteria, have no IEs up to and including the Week 8 BCVA assessment and complete 8 weeks of treatment of study drug (given as a single ophthalmic IVT injection every 4 weeks/monthly).

IEs are defined as:

- Early discontinuation of study treatment. Subsequent missing data (missing or collected) will be imputed in the analysis with a hypothetical strategy.
- Non-adherence with the protocol which would potentially affect the efficacy results. Such identified data at the BDRM (missing or collected) will be imputed in the analysis with a hypothetical strategy.
- Start of anti-VEGF treatment in the fellow eye. Subsequent data (missing or collected) will be imputed in the analysis with a hypothetical strategy.

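### Section 8.3.5 gives the treatment-failure stop to a role that 8.4.1 describes as unmasked; it should name the masked investigator

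*Combined protocol and SAP*

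**What the plan says.** Section 8.3.5 gives nine reasons for stopping study drug. One is "Treatment failure, as assessed by the treating investigator". No threshold of letter loss, OCT rule or confirmation step is attached to it.

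The role appears once more, in 8.4.1: "the PI must delegate tasks to an unmasked treating investigator and ample unmasked support staff".

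Section 8.4.6 sets out the masking. It states "Masked study team members will perform efficacy assessments", allows the unmasked injector only the injection and the immediate safety checks, and permits no overlap between masked and unmasked staff. It treats the ordinary investigator as masked: "Randomization information for any particular subject may be made available to the investigator only in the event of a medical emergency", or for an adverse event that requires the drug to be identified. It does not say who decides on stopping.

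Section 8.4.7.1 leaves removal of a subject who needs rescue treatment to the Principal Investigator.

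For the primary estimand, 11.3.3.1 lists as an intercurrent event "Early discontinuation of study treatment. Subsequent missing data (missing or collected) will be imputed in the analysis with a hypothetical strategy". It adds that the design plans no assessments after treatment is stopped early. Section 11.3.3.2 carries the same estimands over to the secondary endpoints. Section 11.3.7 assumes MAR for the main analyses and plans sensitivity analyses under missing not at random (MNAR).

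**The concern.** Deciding that treatment has failed is a judgement about efficacy in substance, even if it is not a measurement. The caps and stoppers of the two products differ in color and length (8.4.6), so the person who prepares or injects the drug does know the arm. If that person also decides who has failed, with no criterion to limit the decision, the threshold for stopping can differ between arms without anyone intending it.

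The route to the analysis is short. A stop ends the scheduled readings, and what would have followed is predicted from earlier data under MAR. If poor responders were stopped more readily in one arm, for reasons not fully captured in their recorded BCVA, that arm's later means would be too high. With a masked decision, the same selectivity would act alike in both arms and would largely cancel in the difference. Section 11.3.3.1 itself warns that intercurrent events in a biosimilarity study can dilute a difference and favor equivalence.

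**Working it through.** **1. Who decides what**

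| Decision | Section | Decision-maker | Masking status in the text |
|---|---|---|---|
| Stop for an adverse event; investigator request | 8.3.5 | the investigator | treatment code only in an emergency or for a safety need (8.4.6) |
| Removal for need of rescue | 8.4.7.1 | Principal Investigator | not stated outright; delegates unmasked tasks to others (8.4.1) |
| Stop for treatment failure | 8.3.5 | treating investigator | described as unmasked (8.4.1) |
| Efficacy assessments | 8.4.6 | masked team members | masked |

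Treatment failure is the only stopping reason tied to the role that 8.4.1 calls unmasked.

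**2. Which readings are exposed**

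Thirteen doses every 4 weeks fall at Weeks 0, 4, ..., 48, so 12 come after baseline. Week 8 BCVA is read before the Week 8 injection (9.2.4). Only the Week 4 dose precedes that reading; the other 11 do not. After the Week 4 dose, the next one to withhold is at Week 8, and a decision taken at that visit does not lose the primary reading. It is lost only if the subject is stopped at or before the Week 4 dose, or is withdrawn between visits. Of the six secondary BCVA time points (Weeks 4, 12, 16, 24, 36, 52), five come after Week 8.

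**3. Background: the plan's power figure**

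Inputs from 11.4: 580 subjects (290 per arm), SD 10, margin 3.5, 95% CI. SE = 10 × √(2/290) = 0.830. At a true difference of 0, power = 2Φ(3.5/0.830 − 1.96) − 1 = 97.6%, consistent with the stated >90%. At a true difference of 0.5 letters it is 94.9%. The present point does not rest on these figures.

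**4. Shift at Week 8**

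The documents give no treatment-failure rate, so the following are assumptions: 290 in the arm; SD 10 at Weeks 2, 4 and 8; correlation 0.6 to 0.8, compound symmetric or AR(1); k = 3 to 9 excess stops (3/290 = 1.0%, 9/290 = 3.1%), all in one arm, each losing its Week 8 value but keeping Weeks 2 and 4. The MAR estimate is the mean of the observed Week 8 values and, for the k missing, the regression prediction from Weeks 2 and 4 fitted to those who remain. The k subjects with the lowest expected Week 8 value are stopped. The cases differ in how much the decision-maker knows beyond the recorded BCVA. Insight is the correlation of that knowledge with the unexplained part of the Week 8 outcome, whose SD runs from 10√(1 − 2×0.8²/1.8) = 5.4 (compound symmetric, 0.8) to 10√(1 − 0.6²) = 8.0 (AR(1), 0.6). There were 4,000 simulated arms per setting.

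| Insight beyond recorded BCVA | 3 stops (letters) | 9 stops (letters) |
|---|---|---|
| None | 0.00 | 0.00 |
| 0.3 to 0.5 | 0.01 to 0.06 | 0.03 to 0.18 |
| Perfect foresight (upper bound) | 0.08 to 0.18 | 0.23 to 0.48 |

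Against the margin, 0.18/3.5 = 5% and 0.48/3.5 = 14%.

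**5. Shift at Week 52**

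If k stopped subjects would truly have been d letters below their MAR prediction, the arm mean shifts by k × d/290. With d assumed to be 5 to 15 letters, this runs from 3 × 5/290 = 0.05 to 9 × 15/290 = 0.47 letters. No margin applies there.

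**The case against.** **Loose wording.** The treating investigator is not a defined role. Section 8.4.1 adds the adjective unmasked, which would be unnecessary if the term already implied it, and the list of unmasked staff in 8.4.6 does not use the term. Section 8.4.7.1 suggests that the sponsor meant such decisions to lie with the Principal Investigator. This stands, and it rules out calling the point a proven masking failure. It does not remove the need for a correction: a site that follows the text has only 8.4.1 to tell it who the treating investigator is.

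**A direct contradiction.** A reader might infer that 8.3.5 contradicts 8.4.6. The documents do not support that. The efficacy variables in 10.1.1 are BCVA, foveal thickness, OCT morphology, and leakage and lesion size; treatment failure is not among them, and masked staff still measure all of them. The inconsistency is with the intent of 8.4.6.

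**The only efficacy-based stop.** A reader might also infer this. It goes too far: investigator request and sponsor request are equally open-ended and could cover a poor response.

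**Existing safeguards.** Readings before the stop are kept, 9.2.10 provides a visit at the time of early withdrawal, and MNAR sensitivity analyses are planned. Withdrawal reasons go into the eCRF (8.3.5), and early terminations are summarized with reasons (11.3.1), so an arm imbalance would be visible. These limit the problem and make it detectable. None of them supplies the readings at later scheduled visits.

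**Generous Week 8 assumptions.** Given the timing in step 2 of the check, 3 to 9 excess stops in one arm before the Week 8 reading is a severe case. This stands, and it is why the Week 8 effect is judged negligible.

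**Conclusion.** The point holds as a minor masking correction. As written, 8.3.5 can be followed in a way that lets an arm-aware person trigger, without any criterion, an intercurrent event after which data are imputed.

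A reader might infer that the Week 8 equivalence conclusion is at risk. It is not: the shift is zero if stops depend only on recorded BCVA, at most 0.18 letters with partial further insight, and below 0.5 even with perfect foresight, against 3.5. What exposure there is lies with the supportive endpoints from Week 12 to Week 52, where 0.05 to 0.47 letters is possible at Week 52. That range simply follows from the assumed stops and the assumed 5 to 15 letter deficit, and no decision rule depends on it.

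The textual part rests on the two uses of the role name. The sizes rest on assumed stop counts, correlations and deficits, because the documents give no failure rate. Severity is low.

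**What to change.** In 8.3.5, reword the item as: *Treatment failure, as assessed by the masked investigator (not the unmasked treating investigator/injector)*. This agrees with 8.4.6 and with the handling of rescue in 8.4.7.1. Nothing else changes.

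The cost is a one-line amendment. The small downside is that the masked investigator must make and document the decision. The rewording does not supply a criterion for failure; it only ensures that whoever exercises the discretion does so without knowing the arm.
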